Statistical analysis was conducted using IBM SPSS Statistics for Windows, version 25.0 (IBM Corp., Armonk, NY, USA). Data normality was evaluated using the Shapiro–Wilk test. For normally distributed and homogeneous data, one-way analysis of variance (ANOVA) was applied. When the data were not normally distributed but homogeneous, the Kruskal–Wallis test was used. Comparisons across three time points were performed using repeated-measures ANOVA, with the Friedman test employed as the nonparametric alternative.

REFERENCE

ARIA (Allergic Rhinitis and its Impact on Asthma). 2019. ARIA guideline 2019: treatment of allergic rhinitis in the German health system. Allergol Select. 2019 Dec 30;3(1):22-50. doi: 10.5414/ALX02120E. PMID: 32176226; PMCID: PMC7066682.

Bjermer, Leif; Westman, Marit; Holmström, Mats; Wickman, Magnus C. (2019). The complex pathophysiology of allergic rhinitis: scientific rationale for the development of an alternative treatment option. *Allergy, Asthma & Clinical Immunology*, 15(1), 24 – . doi:10.1186/s13223-018-0314-1

Dalimartha, S. & Adrian, F. (2013). Fakta Ilmiah Buah & Sayur. Jakarta: Penebar Swadya.

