IL 8 plays an important role in acute inflammation because it acts as a potential chemotactic agent and neutrophil activator by activating CXCR1 and CXCR2 (Emadi et al., 2005). The reduced IL 8 response induced by LPS in neutrophils has been confirmed in human whole blood translational and non-animal models. This was achieved by exposing neutrophils in vitro to a pro-inflammatory microenvironment containing N-formyl Met Leu Phe, LPS, or IL 8, resulting in a response accompanied by an increase in cell size and pH that leads to a decrease. The detailed kinetics of this degradation can be shown almost in real time by measuring flow cytometry. Overall, we provide a new mechanistic overview of the interaction between IL 8 and neutrophils and explain how IL 8 changes during systemic inflammation.

Meanwhile, MKK6 phosphorylates another MAPK, p38, which leads to the phosphorylation of MK 2 and stabilizes IL 8 mRNA. The activation of the C/EBP signaling pathway is largely still unknown (Matsushima et al., 2022).

CHAPTER III

RESEARCH METHOD

A. Type of Research The type of research used is Clinical Experimental, designed with a Randomized Controlled Trial double blind, with pre and post test design on samples of patients with persistent allergic rhinitis.

B. Place and Time of Research The research is conducted at the Outpatient Clinic of Ear, Nose, Throat Health Science Surgery at the Sebelas Maret University Hospital and the biomedical laboratory of the Faculty of Medicine UNS for the examination of MDA, NF kB, TNF α , Interleukin 6, Interleukin 8. The research will be carried out after obtaining research approval from the dissertation proposal examination board and the Research Ethics Commission.

C. Subjects/Sample of Research Outpatient patients who have undergone anamnesis and physical examination of ENT.

1. Restriction Criteria **Inclusion Criteria:**

- 1) Patients aged 18 – 60 years who have signed informed consent
- 2) Diagnosed with persistent allergic rhinitis with Skin Prick Test or Positive IgE Examination.

Exclusion Criteria:

- 1) The presence of complications in the nose such as nasal septum deviation, polyps, rhinosinusitis
- 2) Have undergone specific immunotherapy for 2 years
- 3) Use of medications that affect allergy test results: antihistamines, corticosteroids, antihypertensive medications, and decongestants
- 4) Pregnancy and Breastfeeding.

Sample Size

The sample size uses the Frederer formula.

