$$\text{Frederer Formula} = (n - 1) (t - 1) \geq 15$$

Explanation: n: sample size of each group: number of groups

According to the Frederer formula, the number of samples required:

$$(n - 1) (t - 1) \geq 15(n - 1) (3 - 1) \geq 15(n - 1) 2 \geq 152n = 17, n = 8.5$$

The number of samples used must be greater than or equal to 9 samples per group. In this study, 10 test samples will be used in each group. This is done to facilitate the author in data analysis calculations, so the total number of samples used in this study is 40 samples.

Sampling Technique

Randomized Control Trial pre and post-test design. Eligible participants/patients who meet the inclusion and exclusion criteria will be randomized. Participants will be grouped into four groups, namely the control group and the treatment group, and then the outcomes will be observed.

F. Implementation/Research Procedure

1. Recruitment of research subjects and randomizationAll patients with persistent allergic rhinitis, Randomization with closed envelopes, Therapy according to the persistent allergic rhinitis algorithm
2. Source of apple fruit extractApple fruit extract is made in the Pharmacy Laboratory of Muhammadiyah University of Surakarta.

3. Preparation of apple fruit extract Polyphenol extract is derived from the fruit of *Mallus sylvestris* mill obtained from apple farmers in Malang. Dried apples are extracted, and re-extracted twice with 50% ethanol. The obtained material is concentrated using a rotary evaporator (Rotavapor, Buchi Labortechnik AG, Switzerland) in a water bath at 40 °C. Furthermore, the extract is adsorbed using Amberlite XAD 16 resin (Brentag, Essen, Germany), and after the evaporation of ethanol, the collected fraction is dried in a vacuum oven SPT 200 (Zeamil, Krakow, Poland) (Mihailović et al., 2018).
4. Measurement of Malondialdehyde (MDA)Measurement of MDA using the Enzyme Linked techniqueItchy noseClinical symptoms in allergic rhinitis.TNSS Checked on the First day and the 14th dayOrdinalRhinorrheaClinical symptoms in allergic rhinitis.TNSS Checked on the First day and the 14th dayOrdinal.

G. Statistical Analysis

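### At least seven outcomes, no primary outcome named in the supplied text, and no control of error across outcomes in Section G

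*Combined protocol and SAP*

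**What the plan says.** Chapter III, Section B assigns the biomedical laboratory "for the examination of MDA, NF kB, TNF α , Interleukin 6, Interleukin 8". The part of the variable table that survives at the end of Section F lists itchy nose and rhinorrhea as separate ordinal variables: "TNSS Checked on the First day and the 14th dayOrdinalRhinorrheaClinical symptoms in allergic rhinitis".

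On design, Sampling Technique states "Participants will be grouped into four groups, namely the control group and the treatment group". Sample Size states "In this study, 10 test samples will be used in each group" and "the total number of samples used in this study is 40 samples". The sample size comes from a resource formula that refers to no outcome, effect size, significance level or power.

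Section G begins "Statistical analysis was conducted using IBM SPSS Statistics for Windows, version 25.0" and then describes tests by type of data only: "For normally distributed and homogeneous data, one-way analysis of variance (ANOVA) was applied", with Kruskal-Wallis as the rank-based alternative. It adds: "Comparisons across three time points were performed using repeated-measures ANOVA, with the Friedman test employed as the nonparametric alternative". It lists no variables, gives no significance level, ranks no outcome, and names neither a post-hoc procedure nor an adjustment for multiple testing.

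**The concern.** With seven or more outcomes and no rule saying which one decides the trial, any of them can become the headline once the results are known. An ineffective extract then has a larger chance of yielding some significant finding than the level of any single test suggests. A reader of the report could not tell a planned finding from one picked out of many. The analysis day is open in the same way, because the surviving table shows two symptom assessments while Section G compares three time points. This cannot be repaired after the data have been seen.

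**Working it through.** **Inputs from the documents.** Five laboratory markers (Section B); two visible symptom items (Section F); so k = 5 + 2 = 7. Four groups of 10, total 4 × 10 = 40 (Sample Size, Sampling Technique).

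**Assumptions.** Significance level 0.05 per test; one omnibus test per outcome; every listed outcome tested. Section G states none of these. For the comparisons with control, one arm is taken as control and the other three as treatment arms, and a lower value counts as favourable.

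**The plan's own figure.** (n − 1)(3 − 1) ≥ 15 gives n = 8.5, rounded up to 9, with 10 used; this reproduces. The formula uses three groups and the trial has four. With four, (n − 1) × 3 ≥ 15 gives n = 6. That mismatch should be reconciled but does not affect this point. The calculation identifies no primary outcome.

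**Independent outcomes.** Chance of at least one significant result = 1 − 0.95^k:
- k = 5 (markers only): 22.6%
- k = 6 (the two symptom items replaced by one TNSS score): 26.5%
- k = 7: 30.2%

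**Correlated outcomes.** Simulation with 10,000 runs, normal data, four groups of 10, seven one-way ANOVAs at 0.05 and a common correlation between outcomes:

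| Correlation | Any significant omnibus test | Significant omnibus test and an arm significantly lower than control | Any of three unadjusted comparisons with control |
|---|---|---|---|
| 0 | 30.2% | 13.3% | 60.4% |
| 0.3 | 28.7% | 12.6% | 55.7% |
| 0.5 | 24.1% | 10.7% | 48.9% |
| 0.7 | 19.3% | 8.5% | 39.8% |
| 0.9 | 11.8% | 5.1% | 26.2% |

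The last column counts differences in either direction. With separate correlations within markers, within symptoms and between the two sets, the omnibus figure was 27.8% (0.3/0.5/0.1), 26.6% (0.5/0.5/0.2) and 22.7% (0.7/0.6/0.3).

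**Benchmark for the stricter rule.** The middle column should not be compared with 5%. From the independent case, one outcome under that rule gives 1 − (1 − 0.133)^(1/7) ≈ 2.0%. Seven outcomes therefore multiply the error by about 13.3/2.0 ≈ 6.7 when independent and 5.1/2.0 ≈ 2.6 at correlation 0.9.

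**After a fix.** One primary outcome with one omnibus test at 0.05 gives 5%. For comparison, Bonferroni over seven outcomes uses 0.05/7 = 0.00714 each, and 1 − (1 − 0.00714)^7 = 4.9%.

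**The case against.** A reader might infer that an inert extract has a one-in-four chance or more of producing a result that can be reported as success. The documents do not support that.
- The 24% to 30% counts any significant four-arm omnibus test, including one where an arm looks worse than control or where two treatment arms differ only from each other. Requiring an arm significantly lower than control gives about 5% to 13%.
- One in four is not a floor. The background describes a shared pathway in which NF-kB drives transcription of the cytokines, so high correlation among the markers is plausible. At 0.7 to 0.9 the omnibus figure is 12% to 19%.
- The 0.05 level is assumed, and Section G does not list the variables it tests. Testing all of them is an inference, though Section G excludes none and offers no other analysis.

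The supplied text also has gaps: most of the variable table is lost and no objectives section survives. A primary outcome may be named elsewhere, so its absence can be asserted only for the text at hand. The symptom items are ordinal, so the ANOVA simulation only approximates the Kruskal-Wallis test that Section G would offer for them.

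Finally, this is a 40-patient dissertation study that does not call itself confirmatory. That is fair, and labelling every outcome exploratory would answer the point. The plan does not do so either.

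What stands is that Section G, which reads as complete, has no outcome hierarchy and no error control. The five markers in Section B are enough to raise the issue without the damaged table.

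**Conclusion.** The point holds in a limited form. At least seven outcomes are measured, none is named primary in the supplied text, and Section G does not control error across them. At an assumed 0.05 with one omnibus test per outcome, the chance of at least one significant result with an inert extract is about 12% to 30%, depending on correlation. It is about 5% to 13% if an arm must also be significantly lower than control, against about 2% for a single outcome under the same rule.

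Unadjusted pairwise tests would raise these figures, as the last column of the table shows. So would the time-point tests: Section F lists guideline-type therapy at recruitment, so patients may change over time whatever the extract does. The size rests on the assumed level and correlations; the missing hierarchy and adjustment do not.

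**What to change.** In Section G, before data are seen:
- State the significance level.
- Name one primary outcome, one analysis day and one between-group test. The four-arm omnibus test at 5% is suitable, with any arm-versus-control comparisons adjusted (Dunnett, or Holm on rank tests if the outcome is ordinal). Saying only two-sided 5% would not be enough with four arms: three unadjusted comparisons with control on a single outcome give about 12.5% by simulation.
- Day-14 TNSS is a reasonable candidate, because the opening background motivates the trial by complaints that persist under standard therapy. The choice belongs to the investigators. If a total score is used, define it.
- Treat the five laboratory markers as one secondary family with Holm adjustment: ordered p-values against 0.05/5 = 0.01, then 0.0125, 0.0167, 0.025 and 0.05.
- Label everything else exploratory and rest the efficacy conclusion on the primary outcome alone.
- Reconcile the three time points in Section G with the first-day and day-14 TNSS assessments in Section F.

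Section G is written in the past tense. If data have already been seen, report all results as exploratory instead.

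The cost is a few sentences. Secondary p-values become somewhat less favourable, and a striking secondary result can no longer carry the conclusion.

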Data from the AR patients in the ENT outpatient unit at the Sebelas Maret University Hospital, Surakarta, shows that the number of new AR cases in 2023 is 103 (37%) cases, and old cases are 170 (62%) cases. The number of new cases up to April 2024 is 159 (36%) cases, and old cases are 273 (63%) cases. This data indicates that the number of old cases each year is greater than the number of new cases, which shows.

2 that long-term patients still experience complaints and still come for treatment. This may be caused by the standard therapy used not being maximal in addressing

complaints comprehensively, thus complementary therapy is still needed to address RA symptoms. Complementary treatment is a group of additional medical care using modalities or products that are not included in conventional medicine, which are used on patients with allergic diseases including RA. Various complementary therapies for RA include acupuncture, herbal medicine, homeopathy, and physical therapy.

Pathogenetically, inflammation in RA begins with the sensitization phase, rapid allergic reaction phase (RAFC), and slow allergic reaction phase (RAFL). In RAFC, mast cell degranulation occurs, resulting in the production of several mediators such as histamine, prostaglandin, and leukotriene. In RAFL, infiltration of several inflammatory cells such as eosinophils occurs due to ICAM 1 (Intercellular adhesion molecule 1) molecules. Subsequently, several inflammatory cytokines such as interleukin (IL) IL 4, IL 6, Tumor Necrosis Factor Alpha, and others are produced. The pathway for cytokine and inflammatory molecule formation is through cytokine gene transcription by NFkB (Nuclear factor kappa B) in the cell nucleus. The activators of NFkB include oxidant free radicals, namely ROS (Reactive oxygen species) such as air pollution. In research that has been conducted, an increase in NFkB expression and mRNA ICAM 1 in the nasal mucosa of RA patients was observed (Zhao et al, 2008).

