Rhinitis comes from the word rino which means nose or nasal and itis which means inflammation or inflammatory. Allergic rhinitis is an inflammatory disease of the nasal mucosa characterized by symptoms such as frequent sneezing, a blocked nose, nasal pruritus or itching in the nose, and clear rhinorrhea or discharge from the nose (Bousquet et al., 2020). The inflammatory reaction in allergic rhinitis is caused by an allergic reaction in patients with a history of atopy who have previously been sensitized to the same allergen (Kasim et al., 2020). In addition to symptomatic symptoms in the nose, patients with allergic rhinitis may also experience allergic conjunctivitis, nonproductive cough, dysfunction of the eustachian tube, and chronic sinusitis (Akhouri & House, 2022).

b. Classification

Initially, allergic rhinitis (AR) was divided into several classifications based on the time of exposure, becoming seasonal (occurring in certain seasons), perennial (occurring throughout the year), and occupational. This classification then changed to the latest clarification according to the guidelines of The Allergic Rhinitis and Its Impact on Asthma (ARIA). The ARIA guidelines classify allergic rhinitis based on the duration of symptoms and the severity of symptoms. The classification of AR based on symptoms according to ARIA is as follows:

1. Intermittent: classified as allergic rhinitis with symptoms ≤ 4 days per week or lasting ≤ 4 weeks.
2. Persistent: defined as allergic rhinitis with symptoms >4 days per week and duration >4 weeks.

Whereas based on the severity of allergic rhinitis symptoms, it can then be classified into:

1. Mild: Can sleep normally No disturbances during daily activities, sports, and relaxation Works and studies normally No bothersome complaints
2. Moderate to Severe: Sleep disturbed There are disturbances during daily activities, sports, and relaxation Disturbances while working and studying There are bothersome complaints

Figure 2.1. Classification of Allergic Rhinitis According to ARIA (Klimek et al., 2019)

Note: Classification of AR based on symptoms according to ARIA.

Intermittent: classified as allergic rhinitis with symptoms ≤ 4 days per week or duration ≤ 4 weeks, Persistent: defined as allergic rhinitis with symptoms >4 days per week and duration >4 weeks.

Epidemiology of Allergic Rhinitis

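### Entry requires no minimum symptom level, so patients with a low day-1 TNSS can be randomised and will dilute the symptom comparison at 10 per group

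*Combined protocol and SAP*

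**What the plan says.** Chapter III, C.1 (Restriction Criteria) has two inclusion criteria. The first is "Patients aged 18 – 60 years who have signed informed consent". The second is "Diagnosed with persistent allergic rhinitis with Skin Prick Test or Positive IgE Examination". The four exclusions concern nasal complications, immunotherapy, drugs that interfere with allergy testing, and pregnancy or breastfeeding. None refers to symptom intensity. The Sampling Technique section adds no further screen: "Eligible participants/patients who meet the inclusion and exclusion criteria will be randomized".

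Chapter II, A (Allergic Rhinitis, b. Classification) separates two axes. One is duration: "Persistent: defined as allergic rhinitis with symptoms >4 days per week and duration >4 weeks". The other is severity, whose lower class reads "Mild: Can sleep normally No disturbances during daily activities, sports, and relaxation Works and studies normally No bothersome complaints".

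In the outcome table in Chapter III, F, the legible symptom rows (itchy nose and rhinorrhea) carry the entry "TNSS Checked on the First day and the 14th dayOrdinal". The recruitment item of the same section also places patients on therapy under the algorithm for persistent disease, and does not limit this to one group. Chapter III, G compares groups by one-way ANOVA or Kruskal-Wallis and time points by repeated-measures ANOVA or Friedman. It mentions no baseline adjustment.

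The background section justifies the trial by the observation that "long-term patients still experience complaints and still come for treatment".

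**The concern.** A symptom score has a lower bound. In a pre/post design, a patient can fall only by the points held on day 1. If low scorers are admitted, the effect seen in them is cut short, and the average difference between groups shrinks although the treatment works equally well in everyone. With 10 patients per group there is little power to spare. Two features of the plan add to this. Background therapy may take low scorers to the bottom of the scale before the extract can add anything. And with no adjustment for the day-1 score, a chance imbalance in the number of low scorers shifts the comparison. A null symptom result could then not separate an inactive extract from a sample with little left to improve. The entry rule also does not select the still-symptomatic patients on whom the rationale rests.

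**Working it through.** **1. The plan's own figure.** The sample-size rule is (n − 1)(t − 1) ≥ 15. With the plan's t = 3, n ≥ 15/2 + 1 = 8.5, rounded up to 9. The plan uses 10 per group, and 10 × 4 groups = 40. Both figures reproduce. (The rule is run with t = 3 although four groups are described; with t = 4 it gives n ≥ 15/3 + 1 = 6.) The rule contains no alpha, power, effect size, SD or symptom score, so it offers no protection against dilution of the TNSS effect.

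**2. Can low scorers enter?** Set side by side, the eligibility list requires persistence and a positive allergy test, while the classification defines persistence by days per week and weeks only. Mild persistent patients meet every legible criterion, and so does anyone with a low day-1 TNSS.

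**3. How much effect survives near the bottom?** The legible text gives no TNSS range, SD, expected effect or severity mix, so everything from here on rests on assumptions. Assume a 0-12 score, a control fall of 1, a true extra fall of 2 on treatment, noise SD 1.5, and scores rounded and cut off at 0 and 12.

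| Day-1 score | Observed group difference (true value 2) |
|---|---|
| 0 | 0.20 |
| 1 | 0.53 |
| 2 | 1.00 |
| 3 | 1.47 |
| 4 | 1.79 |
| 6 | 1.99 |

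The effect is compressed steadily below about 4. Only at 0 is a fall impossible; the 0.20 there comes from less worsening than in controls.

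**4. What does this do to power at 10 versus 10?** Assume a 0-12 score, a true fall of 3, SD of change 2, baseline about 8 (moderate-severe) or 2 (mild), and a t-test on change at two-sided 0.05. Check without a floor: standardised effect 3/2 = 1.5, noncentrality 1.5 × √(10/2) = 3.35 on 18 degrees of freedom, power 0.887. The simulated 0.88 agrees.

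| Share mild | Power, no background improvement | Power, both arms also fall 2 points |
|---|---|---|
| 0% | about 0.88 | about 0.88 |
| 25% | about 0.84 | about 0.70 |
| 50% | about 0.78 | about 0.52 |

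These figures move by a few hundredths with the assumed spread of baseline scores.

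**5. A second model.** Keep the step 3 assumptions, with mild baselines 1-3, other baselines 5-10, and a Mann-Whitney test on change. Power is about 0.76, 0.72, 0.67 and 0.60 at 0%, 10%, 25% and 50% mild. The direction is the same and the size is again moderate.

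**The case against.** A reader might infer that TNSS cannot register any improvement in mild patients. The documents do not support that, for two reasons. First, it is true only at a score of exactly 0. In a run of the step 4 model without background improvement, the mean observed difference was 2.86 with no mild patients and 2.03 with 75% mild. Mild patients therefore contributed (2.03 − 0.25 × 2.86)/0.75 = 1.75 points, or 1.75/2.86 = 61% of the full effect. Second, the plan defines mild by sleep, activity, work and bother, not by a nasal score. Persistent disease needs symptoms on more than 4 days a week for more than 4 weeks, and users of antihistamines, corticosteroids and decongestants are excluded. Nothing suggests that scores of 0 are common.

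A reader might also look at single items. On an assumed 0-3 item with a true fall of 1 point, power drops from 74% to 32% when the share scoring 0 on day 1 rises from none to 60%. That figure does not fit this point, because a patient with severe disease can score 0 on one item and a total-score threshold would not prevent it.

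Other limits stand. The simulated tests compare two arms on change, whereas Chapter III, G plans tests across groups and over time and does not say that change is analysed. The outcome table is broken, so scoring details may be lost. No primary outcome is legible, and MDA, NF-kB, TNF-alpha, IL-6 and IL-8 are not bounded by a TNSS floor.

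Finally, broad eligibility is a legitimate choice, and stratifying on or adjusting for day-1 TNSS would handle chance imbalance while keeping mild disease in scope. That is right about imbalance, but neither step gives a low scorer more room to improve.

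**Conclusion.** The concern holds as dilution of the symptom comparison. The entry rule admits patients with low day-1 TNSS, and the planned analysis does nothing to offset it. The size depends on the severity mix, which the documents do not give. Under the step 4 assumptions, the loss at 25% to 50% mild is 0.04 to 0.10 in power (0.88 to 0.84 or 0.78) without background improvement. It is 0.18 to 0.36 (0.88 to 0.70 or 0.52) if both arms also fall 2 points. The second case deserves weight because the procedure section provides background therapy, although the 2-point fall is itself an assumption. The conclusion covers TNSS only. It does not extend to the laboratory outcomes, and it does not show that the trial would miss a real symptom effect. It should be settled before enrolment, since lost room to improve cannot be restored afterwards.

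**What to change.** - **Entry rule.** Add to Inclusion 2 a minimum total TNSS, set before enrolment, high enough to leave room for the improvement the trial hopes to show, and scored before the randomisation envelope is opened. The moderate-to-severe class in Chapter II is an alternative, but it is not defined by nasal score and so controls the floor less directly. State the TNSS range in the protocol.
- **Analysis.** In Chapter III, G, compare day-14 TNSS between groups with the day-1 score as a covariate. Draw no efficacy conclusion from within-group pre-post falls: selecting on day-1 TNSS picks out some temporarily high scores, and regression to the mean then produces falls in every group.

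**Cost.** One eligibility line and one analysis sentence. TNSS is already taken on day 1, but the documents do not say that this precedes randomisation, so the order must be made explicit. Results would no longer cover mild disease. Some patients would be screened out: the clinic reports 159 + 273 = 432 cases up to April 2024 against 40 needed, but these are all allergic rhinitis, and the persistent, unmedicated share is not stated. Zeros on single items can remain.

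If the sponsor prefers to keep mild disease, stratifying by and adjusting for day-1 TNSS is the fallback. It limits imbalance only, and the reduced room to improve should then be acknowledged in the protocol.

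### The eligibility criteria do not exclude patients with a known allergy to apple from a trial of an apple-fruit extract

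*Combined protocol and SAP*

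**What the plan says.** Chapter III, C of the combined protocol and SAP draws subjects from "Outpatient patients who have undergone anamnesis and physical examination of ENT". Under C.1 there are two inclusion items. The first is age 18 to 60 with signed consent; the second is "Diagnosed with persistent allergic rhinitis with Skin Prick Test or Positive IgE Examination".

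The exclusion list has four numbered items. The first is "The presence of complications in the nose such as nasal septum deviation, polyps, rhinosinusitis". The second concerns earlier allergen immunotherapy, with a two-year period attached. The third reads "Use of medications that affect allergy test results: antihistamines, corticosteroids, antihypertensive medications, and decongestants". The fourth and last rules out women who are pregnant or nursing.

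The Sampling Technique section then gives the rule for entry: "Eligible participants/patients who meet the inclusion and exclusion criteria will be randomized". It goes on to divide those patients into four groups, described only as control and treatment. The Sample Size section sets 10 patients per group and 40 in total. Section F.3 describes the product as a polyphenol extract prepared from apple fruit.

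**The concern.** The product is made from a food, and every participant has allergic disease by design, since the second inclusion item requires persistent allergic rhinitis. Whether a candidate already knows that they react to the source fruit is therefore an obvious screening question. The plan's own reference list includes a paper on allergic rhinitis in relation to food allergies. The fourth exclusion suggests that the list already carries precautionary items, so a hypersensitivity line would fit there.

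As the criteria stand, an investigator who follows them exactly has no ground for declining a patient who reports reacting to apple. What is at stake is the safety of that patient. The point does not bear on power, on the type I error rate or on the estimated treatment effect.

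**Working it through.** The plan states no figure on this point, so there is none to reproduce. The check is a reading of each place where a safeguard could stand, followed by a simple count.

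**Eligibility items, Chapter III, C.1**

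| Item | Subject | Covers apple or extract hypersensitivity? |
|---|---|---|
| Inclusion 1 | Age and consent | No |
| Inclusion 2 | Diagnosis of persistent allergic rhinitis, by skin prick test or IgE | No: names no allergen panel and excludes nobody for a food reaction |
| Exclusion 1 | Nasal complications | No |
| Exclusion 2 | Specific immunotherapy | No |
| Exclusion 3 | Medications that affect allergy tests | No |
| Exclusion 4 | Pregnancy, breastfeeding | No |

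The count is 0 of 2 inclusion items and 0 of 4 exclusion items. The exclusion list is numbered 1 to 4 and is followed directly by the Sample Size section, with no sign of a cut or redaction.

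**Other places where a safeguard might stand**

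- Chapter III, C mentions anamnesis and an ENT examination. No question about apple or food allergy is attached to either, and no exclusion follows from the answers.
- Chapter II, Side Effects deals with quercetin's effect on the pharmacokinetics of other drugs. It does not mention allergy.
- The contraindications given in Chapter II for skin testing concern the diagnostic test, not receipt of the extract.
- Chapter III, F.3 describes ethanol extraction, concentration, resin adsorption and drying. It gives no limit for residual protein or allergen.
- Chapter II, Complementary Therapy describes apple polyphenols in general as purified and made up mainly of procyanidins. That does not establish that no allergen remains.

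**Consequence of the entry rule.** Meeting the listed criteria is enough to be randomised. A known reaction to apple breaches none of them, so such a patient is eligible as written.

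**How many patients the missing check covers.** Inputs: 4 groups and 10 per group (Sampling Technique; Sample Size). Total: 4 × 10 = 40. The available text does not say which groups receive extract. Assuming at least one control group and at least one extract group, the number of extract groups is between 1 and 3:

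- minimum: 1 × 10 = 10 patients on extract
- maximum: 3 × 10 = 30 patients on extract

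This counts everyone allocated to extract without the check. It does not estimate how many of them react to apple. The documents give no prevalence, so no probability is attached.

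**The case against.** The strongest reply is that no hazard has been shown. Nothing in the documents says that apple allergy is common in this population or that the extract contains allergen. The preparation includes ethanol extraction and adsorption on resin. The background chapters report that apple polyphenols inhibit degranulation and histamine release, and that a procyanidin fraction may induce oral tolerance in a rat model. Reacting to an apple may therefore not mean reacting to this product. This stands as far as it goes: the danger is unproven. But no place in the documents states that allergen is removed or that apple-allergic patients tolerate the extract, so safety is unproven too.

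A second reply is that the patients at issue know about their reaction and are seen in an allergy-focused clinic, so they would probably disclose it at anamnesis or decline consent. That probably lowers the practical risk. It leaves the decision to individual judgement, where a written rule would settle it.

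Third, a warning may exist in text not available here, such as the consent form or a dosing section. If one bars apple-allergic patients, much of the safety concern falls away, although the eligibility list would still need the line to agree with it.

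Finally, the 10 to 30 count does not measure harm: the number of known apple reactors allocated to extract could be zero. That is correct, and the count should be read only as the number of patients to whom the missing check would apply.

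**Conclusion.** The point holds as a minor, precautionary safety gap. No eligibility item keeps a patient with a known reaction to apple out of a trial of an apple-derived extract. The absence follows directly from the criteria and the entry rule and rests on no assumption. The size of the resulting risk is unknown, because neither the frequency of apple allergy nor the residual allergenicity of the extract is given. The range of 10 to 30 patients out of 40 rests on the assumed split of the four groups.

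**What to change.** Add a fifth exclusion to Chapter III, C.1: *known allergy or hypersensitivity to apple or to any component of the extract*. Make it operational by asking the question at the existing anamnesis and recording the answer before randomisation.

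The cost is one line in the criteria and one question per patient. The sample size calculation and the analysis are unaffected. Some patients will become ineligible; the documents do not allow that number to be stated, though it is likely to be small. They are the patients for whom the safety of the product is undocumented.
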